8.7.1 Onset Date of Adverse Events

The onset date is the date that the event or the signs/symptoms attributed to the event started.

8.7.2 Resolution Date of Adverse Events

The resolution date is the date that the event or the signs/symptoms attributed to the event resolved or resolved with sequelae or it is the date when the patient has reached a new baseline if the event is not expected to resolve.

8.7.3 Intensity of Adverse Events

The severity of each AE will be graded using the NCI CTCAE, v5.0 or later grading scale.⁴²

Severity is not the same as serious.

For AEs not covered by NCI CTCAE, the severity will be characterized as mild, moderate, severe, life-threatening, or fatal according to the following definitions:

- Mild events are usually transient and do not interfere with the patient's daily activities;
- Moderate events introduce a low level of inconvenience or concern to the patient and may interfere with daily activities;
- Severe events interrupt the patient's usual daily activities and hospitalization (or prolongation of hospitalization) may be required;
- Life-threatening events require urgent intervention to prevent death; or
- Fatal events are those events that lead to the patient's death.

8.7.4 Causal Relationship of Adverse Events to Study Drug

Medical judgment should be used to determine the cause of the AE considering all relevant factors such as, but not limited to, the underlying study indication, coexisting disease,

concomitant medication, relevant history, pattern of the AE, temporal relationship to the study medication, dechallenge or rechallenge with the study drug (Table 7).

Table 7. Causal Relationship of Adverse Events to Study Drug

Not Related to Study Drug	
• An AE that is clearly due to extraneous causes (eg, concurrent disease, concomitant medications, disease under study, etc.);• It does not follow a reasonable temporal sequence from administration of the study drug;• It does not follow a known pattern of response to study drug;• It does not reappear or worsen when study drug is restarted; or• An alternative explanation is likely, but not clearly identifiable.
Related to Study Drug	
• An AE that is difficult to assign to alternative causes;• It follows a strong or reasonable temporal sequence from administration of study drug;• It could not be reasonably explained by the patient's clinical state, concurrent disease, or other concomitant therapy administered to the patient;• It follows a known response pattern to study drug; or• It is confirmed with a positive rechallenge or supporting laboratory data.

8.7.5 Outcome and Action Taken

The investigator will record the action taken and outcome for each AE according to the following criteria:

Action Taken with Study Drug (note all that apply)

- Drug withdrawn;
- Dose reduced;
- Dose interrupted;
- Dose not changed;
- Unknown; or
- Not applicable.

Outcome

- Recovered/resolved;
- Recovering/resolving;

- Not recovered/Not resolved;
- Recovered/resolved with sequelae;
- Fatal; or
- Unknown/ Lost to follow-up.

8.8 Follow-up of Adverse Events, Serious Adverse Events, and Adverse Events of Special Interest

All AEs (including SAEs and AESIs) occurring during the study are to be followed up in accordance with good medical practice until resolved; judged no longer clinically significant; or, if a chronic condition becomes the patient's new baseline, until fully characterized through 28 days after the last dose of rucaparib. Any SAEs, AESIs, and treatment-related Grade 3/4 AEs must be followed until resolution or stabilization, death, or until loss to follow-up. After the 28-day safety follow-up window, SAEs considered as potentially related to rucaparib (including serious reports of pneumonitis or similar events, ie, interstitial lung disease, pulmonary fibrosis, acute interstitial pneumonitis, alveolitis necrotizing, alveolitis, hypersensitivity pneumonitis, and organizing pneumonia, if considered to be related to study drug), and the AESIs of MDS and AML irrespective of causality, must be reported.

8.9 Potential Drug-induced Liver Injury

Wherever possible, timely confirmation of initial liver-related laboratory abnormalities should occur prior to the reporting of a potential DILI event. All occurrences of potential DILIs, meeting the defined criteria,⁴⁰ must be reported as SAEs (see [Section 8.7](#) for reporting details).

Potential drug induced liver injury is defined as:

1. ALT or AST elevation $> 3 \times$ ULN
AND
2. Total bilirubin $> 2 \times$ ULN, without initial findings of cholestasis (elevated serum alkaline phosphatase),
AND
3. **No other immediately apparent possible causes** of ALT/AST elevation and hyperbilirubinemia, including, but not limited to, viral hepatitis, pre-existing chronic or acute liver disease, or the administration of other drug(s) known to be hepatotoxic.

8.10 Regulatory Aspects of Serious Adverse Event and Adverse Events of Special Interest Reporting

It is important that the investigator provide an assessment of relationship of the SAE or AESI to study treatment at the time of the initial report. For reporting SAEs/AESIs or pregnancies, use the applicable report forms. The contact information for reporting of SAEs/AESIs or pregnancies can be found on each of the forms.

The sponsor or its designee is responsible for submitting reports of AEs associated with the use of the drug that are both serious and unexpected to the US FDA, according to 21 Code of Federal Regulations (CFR) 312.32; to the European regulatory authorities according to the European Commission Clinical Trials Directive (2001/20/EC); and to other applicable regulatory authorities, according to national law and/or local regulations. All investigators participating in ongoing clinical studies with the study medication will receive copies of these reports for prompt submission to their IRB or IEC. In accordance with the European Commission Clinical Trials Directive (2001/20/EC), the sponsor or its designee will notify the relevant ethics committees in concerned member states of applicable suspected unexpected serious adverse reactions (SUSARs) as individual notifications or through periodic line listings.

The sponsor or its designee will submit all safety updates and periodic reports to the regulatory authorities as required by applicable regulatory requirements.

9 STATISTICAL METHODS

9.1 General Considerations

All statistical analyses will be conducted with the SAS[®] System, v9.4 or higher. Further details around the statistical analyses planned for this study will be outlined separately in the statistical analysis plan (SAP). Changes to or deviations from the SAP will be described in the clinical study report (CSR).

Quantitative variables will typically be summarized using frequencies and percentages for appropriate categorizations and may also be summarized using descriptive statistics. For variables summarized with descriptive statistics, the following will be presented: N, mean, standard deviation, median, minimum, and maximum. Categorical variables will be presented using frequencies and percentages.

The Kaplan Meier methodology will be used to summarize time-to-event variables.

Unless otherwise specified, all data will be used to their maximum possible extent but without any imputations for missing data. Unless otherwise specified, baseline is defined as the last measurement prior to the first dose of rucaparib.

9.2 Determination of Sample Size

Estimated enrollment is from 30 to 220 patients.

Evaluation of efficacy, safety, and tolerability of rucaparib will be focused on patients in Cohort A (patients harboring mutations in certain HRR genes with tumor types that have not been sufficiently evaluated previously in a Clovis-sponsored study of rucaparib monotherapy). The minimum expectation is to enroll 10 or more patients in at least 1 additional tumor type with multiple other tumor types represented with only a few patients each. These additional data could be collected in as few as 30 patients if many of the early enrolled patients are in a single tumor type. Conversely, if the study enrolls patients in a wide variety of tumor types, it may take more than 30 patients to collect data on at least 10 patients in a single tumor type. If enrollment to a given tumor type reaches 11 patients, a futility analysis is planned to gate further enrollment within that tumor type (see [Figure 1](#)). The total study sample size is dependent on enrollment of the various tumor types, risk:benefit assessments throughout the study, and regulatory considerations. If the risk:benefit is favorable, enrollment may reach up to 200 patients in Cohort A for potential regulatory purposes. Combined with the up to 20 patients to be enrolled in Cohort B, the total enrollment could reach a maximum of approximately 220 patients.

9.3 Analysis Populations

The following analysis populations are defined for the study:

- **Safety Population** – The safety population will consist of all enrolled patients who received at least 1 dose of protocol-specified treatment

- **Efficacy Population** – The efficacy population will consist of all patients evaluable for response by RECIST v1.1 (or modified RECIST v1.1/PCWG3 for mCRPC patients)
- **Pharmacokinetic (PK) Population** – The PK population will consist of all patients who received at least 1 dose of rucaparib and had at least 1 PK parameter analyzed.

9.4 Patient Disposition

Patient disposition will be summarized on the Safety Population using frequency counts and the corresponding percentages. The number of patients in each analysis population, number of patients discontinued, and the primary reason for discontinuation will be summarized.

9.5 Demographics and Baseline Characteristics

All demographic (eg, age, race, and ethnicity as allowed by local regulations) and baseline characteristics will be summarized for the Safety Population. The following variables, as appropriate, will be summarized descriptively and/or with frequency tabulations:

- Time since diagnosis (months): ≤ 12 , > 12 to 24 , > 24 ;
- Key baseline laboratory parameters.

9.6 Efficacy Analyses

The analysis of ORR, DOR, and PFS will be based on the RECIST v1.1 criteria (or modified RECIST v1.1 for mCRPC patients) as assessed by the investigator. ORR and DOR will be performed using the Efficacy Population and PFS will be analyzed for the Safety Population.

All patients identified as harboring a reversion mutation in an HRR gene at baseline will be removed from primary and secondary efficacy analyses. Sensitivity analyses will be performed that include any/all patients harboring these reversion mutations. The methodology used to identify patients with a reversion mutation will be specified in a separate document. Sensitivity analyses to investigate the effect of platinum-free intervals (eg, < 3 , 3-6, and > 6 months) and response to previous platinum-based therapy will also be performed. Details of these and all other planned analyses will be described in the SAP.

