The correlation of PALB2 mutations with sensitivity to PARP inhibitors is supported by data from the interim analysis of a maintenance study of rucaparib in pancreatic cancer, where 2 of 2 patients with a PALB2 mutation showed a response.¹³ Additionally, a prostate cancer patient with a deleterious somatic PALB2 mutation remained on treatment with olaparib for 39 weeks.¹⁴

Lastly, secondary reversion mutations in BRCA1 and BRCA2 that restore protein function, reactivate HRR and lead to therapy resistance have been reported in patients following treatment with DNA damaging chemotherapy or a PARP inhibitor, providing strong evidence that the original mutation sensitized the tumor to these agents.^{15, 16} More recently, reversion mutations leading to rucaparib resistance have been identified in RAD51C- and RAD51D-mutated ovarian cancer,¹⁷ and to olaparib resistance in PALB2-mutated prostate cancer,¹⁸ underlining the functional similarities between these 3 genes and BRCA1/2 in determining sensitivity to PARP inhibitors.

Taken together, the evidence described above supports the hypothesis that 1) deleterious mutations in or loss of BRCA1 and BRCA2 induce HRD in cancer cells independent of tissue of origin, leading to rucaparib sensitivity, and 2) RAD51C, RAD51D and PALB2 mutations are additional biomarkers of HRD and predict rucaparib responsiveness in patients with multiple cancer types. Therefore, Clovis (sponsor) anticipates clinical activity of rucaparib in patients harboring a deleterious mutation in one of the genes in this 5-gene panel to be independent of tumor type.

In addition, mutations in other HRR genes, namely BARD1, BRIP1, FANCA, NBN, RAD51 and RAD51B, that are less frequently observed and currently have no or limited clinical evidence of sensitivity to a PARP inhibitor, will also be tested in an exploratory fashion in a smaller cohort of patients.

Primary Objective:

- To determine the objective response rate (ORR), as assessed by the investigator, by RECIST v1.1 (or by RECIST v1.1 and Prostate Cancer Working Group Guidelines Version 3 [PCWG3] criteria in patients with mCRPC).

Secondary Objectives:

- Objective response rate (ORR) as assessed by independent radiology review (IRR) by RECIST v1.1 (or by RECIST v1.1 and PCWG3 in patients with mCRPC);
- DOR;
- Disease Control Rate (DCR), defined as the percentage of CRs, PRs, and SDs greater than 16 weeks;
- PFS;
- Overall survival (OS);
- To evaluate the safety and tolerability of rucaparib;

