2 STUDY OBJECTIVES AND ENDPOINTS

Primary, secondary, and exploratory objectives and endpoints are shown in [Table 1](#).

Table 1. Study Objectives and Endpoints

Objectives	Endpoints	Justifications
Primary Objective	Primary Endpoint	Justification for Primary Endpoint

To determine the ORR by tumor type, as assessed by the investigator, to be evaluated by RECIST v1.1 (or by RECIST v1.1 and Prostate Cancer Working Group Guidelines Version 3 [PCWG3] in patients with mCRPC).
	
Best overall response as assessed by the investigator by RECIST v1.1 (or by RECIST v1.1 and PCWG3 in patients with mCRPC).
	
Best overall response is summarized across patients as ORR, which is the proportion of complete responses and partial responses confirmed in patients with measurable disease and is a direct measure of the drug’s anti-tumor activity. It is commonly used in Phase 2 trials. It excludes stable disease, which may be more reflective of the natural history of the disease rather than response to the investigational drug.

Secondary Objectives	Secondary Endpoints	Justifications for Secondary Endpoints

1. To assess ORR by independent radiology review (IRR).
	
1. ORR as assessed by IRR (irrORR) by RECIST v1.1 (or by RECIST v1.1 and PCWG3 in patients with mCRPC).
	
1. Best overall response as assessed by IRR is summarized across patients as irrORR, which provides a measure of ORR that is devoid of the heterogeneity arising from radiology data being evaluated at various investigational sites and serves as a more independent evaluation of ORR.

2. To assess the duration of response (DOR).
	
2. DOR
	
2. DOR, defined as the time from initial tumor response to documented tumor progression, provides additional information on the longevity of tumor response.

Table 1. Study Objectives and Endpoints

Objectives	Endpoints	Justifications
3. To evaluate DCR.	3. DCR	3. DCR, defined as the percentage of complete response (CR), PR, and stable disease (SD) beyond 16 weeks, is another measure of clinical benefit to the investigational drug, being a composite of SD and ORR.
4. To estimate progression-free survival (PFS).	4. PFS	4. Defined as the duration from entry into study to objective tumor progression or death of a patient, PFS is a measure of clinical benefit.
5. To estimate OS.	5. OS	5. Defined as the duration from entry into study to death, OS is the gold standard for oncology clinical trials.

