3.1.1 Screening Period

All patients will undergo screening assessments up to 4 weeks prior to enrollment.

Screening assessments will include, but may not be limited to, demographics and medical history, prior cancer treatments, prior and current medications and procedures, 12-lead ECG, Eastern Cooperative Oncology Group (ECOG) performance status, hematology and serum/plasma chemistry, urinalysis, physical examination, vital signs measurements, radiologic assessment by computed tomography (CT) or magnetic resonance imaging (MRI). Patients will be required to provide a sample of the most recent archival tumor tissue. If an archival sample is not available, a screening biopsy must be obtained, unless the biopsy location is inaccessible, or the procedure is deemed unsafe by the investigator. The sample will be used for central laboratory confirmation of the mutations; however, receipt of archival tissue or central laboratory results are not required prior to patient starting on study. Data from procedures that are considered standard of care and performed before obtaining patient informed consent for the study may be collected and entered into the electronic case report form (eCRF).

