4.2 Inclusion Criteria

Eligible patients must meet the following inclusion criteria:

1. Have signed an Institutional Review Board (IRB)/Independent Ethics Committee (IEC) approved informed consent form prior to any study-specific evaluation.
2. Be ≥ 18 years of age at the time the informed consent is signed.
3. Have an unresectable, locally advanced (primary or recurrent) or metastatic solid tumor and have relapsed/ progressive disease as confirmed by radiologic assessment.
4. Have measurable disease as defined by RECIST v1.1 ([Appendix 2](#)) or modified RECIST v1.1 and PCWG3 criteria ([Appendix 3](#)) for prostate cancer. A measurable tumor lesion in a previously irradiated site is acceptable if subsequent progression has been demonstrated in that lesion.
5. Have a deleterious mutation (germline or somatic) in BRCA1, BRCA2, PALB2, RAD51C or RAD51D (Cohort A) or a deleterious mutation (germline or somatic) in BARD1, BRIP1, FANCA, NBN, RAD51 or RAD51B (Cohort B). Mutations must be identified by either a local or central laboratory that is certified per Clinical Laboratory Improvement Amendments (CLIA) regulations.
 - a. Mutations may be identified in a tumor tissue, blood, or saliva sample. For a local laboratory test result, the classification of the mutation as deleterious must be documented in the patient's medical record. Variants of uncertain significance or benign variants will not be eligible for enrollment into the trial.
 - b. Patients with EOC, FTC, or PPC must have a deleterious PALB2, RAD51C or RAD51D mutation (or deleterious mutation in another HRR gene, listed in [Appendix 1](#)). Patients with a deleterious BRCA1 or BRCA2 mutation are not eligible.
 - c. Patients with mCRPC must have a deleterious PALB2, RAD51C or RAD51D mutation (or deleterious mutation in another HRR gene, listed in [Appendix 1](#)). Patients with a deleterious BRCA1 or BRCA2 mutation are not eligible.
 - d. Human epidermal growth factor receptor (HER2) negative breast cancer patients with a deleterious germline BRCA1 or BRCA2 mutation are not eligible, unless the use of both olaparib and talazoparib is contraindicated. Breast cancer patients with somatic BRCA mutations are eligible, as are HER2+ patients with deleterious somatic or germline mutations in any of the 11 genes listed in [Appendix 1](#). HER2 negative patients with a deleterious mutation in any non-BRCA HRR gene listed in [Appendix 1](#) are eligible.

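### Section 9.6 drops eligible, treated patients with a baseline HRR reversion mutation from the headline efficacy results; the analysis that includes them should be primary

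*Combined protocol and SAP*

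**What the plan says.** Section 9.6 states the rule: "All patients identified as harboring a reversion mutation in an HRR gene at baseline will be removed from primary and secondary efficacy analyses". It then adds: "Sensitivity analyses will be performed that include any/all patients harboring these reversion mutations". On how carriers are found, it says: "The methodology used to identify patients with a reversion mutation will be specified in a separate document".

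Other parts of the protocol describe a wider group:

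- **Objective (Table 1).** The primary objective is "To determine the ORR by tumor type, as assessed by the investigator", with no restriction on reversion status.
- **Populations (9.3).** "The efficacy population will consist of all patients evaluable for response by RECIST v1.1". The Safety Population is every enrolled patient who took at least one dose. Section 9.6 assigns ORR and DOR to the first and PFS to the second.
- **Eligibility (4.2, criterion 5a).** "Variants of uncertain significance or benign variants will not be eligible for enrollment into the trial". No criterion in 4.2 or 4.3 names reversion mutations.
- **Screening (3.1.1).** For the tissue sample, "receipt of archival tissue or central laboratory results are not required prior to patient starting on study". Section 7.3.6.2 draws blood for ctDNA at screening and before the first dose, but no ctDNA result is required for entry.

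The synopsis background explains why reversions matter. Of such changes in the two BRCA genes, it says that those which "restore protein function, reactivate HRR and lead to therapy resistance have been reported in patients following treatment with DNA damaging chemotherapy or a PARP inhibitor".

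**The concern.** Patients with a baseline reversion can meet every entry criterion, be treated and be evaluable for response. Section 9.6 then takes them out of the primary and secondary efficacy results on the basis of a finding that was not used to select them, and that the sponsor's rationale links to resistance. If carriers respond less often than others, the headline ORR is higher than the ORR of the eligible, response-evaluable patients whom Table 1 and Section 9.3 describe.

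Section 1.2.2 says the study is meant to support a tumor-agnostic indication. The headline should therefore describe the patients whom the entry criteria select. The same section lists frequent reversions among the possible reasons why a tumor type might not respond, which treats reversion as part of that tumor type's responsiveness. The headline ORR by tumor type would remove that component.

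The study is open-label and the primary ORR is investigator-assessed. The text does not say when the identification method is fixed relative to the response data.

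**Working it through.** **1. The plan's own figure.** The only efficacy operating characteristic given is the futility rule in 9.10: 0 responses in 11 patients of a tumor type, a 20% response rate of interest, and a 10% rejection error.

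- P(0 of 10 | 20%) = 0.8^10 = 0.1074
- P(0 of 11 | 20%) = 0.8^11 = 0.0859

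Eleven is the smallest number that brings the error to 10% or less, so the rule reproduces. It counts patients by enrollment and does not refer to the removal in 9.6, so the concern leaves it unchanged.

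**2. Inputs for the effect on ORR.** Let f be the share of evaluable patients with a baseline reversion, p the ORR without one and q the ORR with one. The documents give no value for any of these; all values below are assumptions. From the documents come the sample sizes: up to 200 patients in Cohort A (9.2) and a limit of 50 per tumor type, which may be lifted (3.1).

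**3. Formula.**

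- Headline under 9.6 = p
- Inclusive ORR = (1 − f)p + fq
- Excess = p − [(1 − f)p + fq] = f(p − q)

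**4. Excess with p = 30%, in percentage points.**

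| f | q = 0 | q = 15% | q = p |
|---|---|---|---|
| 5% | 0.05 × 30 = 1.5 | 0.05 × 15 = 0.75 | 0 |
| 10% | 0.10 × 30 = 3.0 | 0.10 × 15 = 1.5 | 0 |
| 20% | 0.20 × 30 = 6.0 | 0.20 × 15 = 3.0 | 0 |

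**5. Counts with q = 0.** Section 9.6.1 asks for 95% CIs without naming a method; exact Clopper-Pearson intervals are assumed, and all patients are taken as evaluable. Carriers number N × f, and responders are 30% of the rest.

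| N | f | Carriers | Headline (carriers removed) | Inclusive |
|---|---|---|---|---|
| 200 | 5% | 10 | 57/190 = 30.0% (23.6–37.1) | 57/200 = 28.5% (22.4–35.3) |
| 200 | 10% | 20 | 54/180 = 30.0% (23.4–37.3) | 54/200 = 27.0% (21.0–33.7) |
| 200 | 20% | 40 | 48/160 = 30.0% (23.0–37.7) | 48/200 = 24.0% (18.3–30.5) |
| 50 | 20% | 10 | 12/40 = 30.0% (16.6–46.5) | 12/50 = 24.0% (13.1–38.2) |

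**6. What bears on f.** Prior PARP inhibitor treatment is excluded (4.3), and in many tumor types so is progression on or soon after platinum (4.2). Both may keep f low. Platinum-resistant ovarian, fallopian tube and primary peritoneal cancer is admitted (4.2, criterion 6b), so f may differ between tumor types. The exclusion could then shift some tumor types' ORR more than others.

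**The case against.** The strongest reply is that this is a choice of target population and not an error. The exclusion is prespecified and rests on a baseline feature. It also has a biological reason: a tumor with a reversion may no longer have the repair deficiency under test. An inclusive sensitivity analysis is planned, and Table 1 and 9.9 already plan efficacy by resistance-mutation status. No success threshold exists to be crossed, the size is wholly assumed, and the intervals overlap heavily.

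Much of this stands. Nothing is concealed, materiality is not demonstrated, and the separate method document cannot be judged from the text, so its timing is unknown and not shown to be late. The biological question is legitimate, but it is already an exploratory objective, and reversion was not made an entry criterion. Naming a reversion-free population in 9.3 would align the labels, yet the headline would still omit patients whom the entry criteria admit. If f is low, including carriers costs almost nothing.

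Two smaller points are also fair. The Efficacy Population itself leaves out non-evaluable patients, so the inclusive ORR describes eligible, response-evaluable patients and not everyone treated. The general exclusion for conditions that may interfere with interpretation (4.3, criterion 12) could in principle be applied to a carrier, but it is an investigator-judgment clause that does not mention reversions.

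**Conclusion.** The concern holds. Section 9.6 removes patients whom 4.2 and 4.3 admit and whom Table 1 and 9.3 include, and the likely effect is a higher headline ORR. The direction rests on carriers responding less often, which the protocol's rationale supports without giving a size. With a 30% ORR in non-carriers, the assumed range runs from zero (carriers respond equally) through 0.75 points (f = 5%, q = 15%) to 6.0 points (f = 20%, q = 0). No final decision flips and the futility rule is unaffected. The change should be made, because it is cheap and aligns the headline with the population the protocol defines; confidence is medium because prevalence and carrier response are unknown.

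**What to change.** Reword 9.6 so that the primary and secondary efficacy analyses use the 9.3 populations with carriers included: the Efficacy Population for ORR and DOR, the Safety Population for PFS. Sections 9.6, 9.6.2.2 and 9.6.2.4 name no population for DCR and OS; whichever is used, carriers should stay in. Make the reversion-excluded analysis the sensitivity analysis. State that the separate identification document is finalized before response data are summarized. Section 9.10 needs no change.

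The cost is wording in 9.6. Both analyses are already planned and no new data are needed. The downside for the sponsor is that the headline ORR may be slightly lower.
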